#### 2.2.5 Power Calculation

The study aims to investigate significant differences in atrial strain values between subjects with atrial fibrillation (AF), hypertension (no AF), and healthy volunteers. To

achieve statistical power for this study, a large enough sample size must be obtained. This will be achieved via the use of power calculations utilising G\*Power 3.1 Statistical support has been provided and a sample size calculation was based on data found within the literature and involved detecting the smaller difference of left atrium contractile % between subjects with atrial fibrillation and healthy volunteers. The following criteria will be utilised: alpha level of 0.05, beta level of 15% and statistical power of 85%. Hence using this minimum value to determine our sample size (expected difference of 4.0, power = 0.85 and SD  $\pm$  7.5) and one-way ANOVA at three levels, a minimum sample size of at least 78 subjects in each group will be required for this study, total of 234 participants required. See Appendix Figures 1 & 2 for power calculation plots.

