# **1. Introduction**

Atrial fibrillation (AF) is the most prevalent type of arrhythmia within an adult population and is characterised by disorganised, chaotic, electrical activity and thus ineffective atrial contraction causing irregular ventricular contraction (Wyndham, 2000). AF can be categorised into three different groups: paroxysmal, persistent, and permanent. The prevalence of AF increases with age and is associated with, but not limited to, a range of risk factors including hypertension, obesity, and alcohol consumption (Staerk, *et al.*, 2017). There is a plethora of both cardiac and non-cardiac causes of AF and the cause is not always clear for each patient. Furthermore, causes of AF can also present as the by-product of AF, this increases the difficulty in determining the individual patient's cause of onset. A diagnosis of AF can be incidental as not all patients are symptomatic. If AF goes undetected, this puts the patient at an increased risk of blood clot formation and stroke (Markides and Schilling, 2003).

Patients suspected of having AF are routinely referred for a transthoracic echocardiogram (TTE). It is common for AF patients to have a dilated left atrium (LA) and this can be visually confirmed in addition to the LA area and volume measurements (Van De Vegte, et al., 2021). However, as LA measurements are limited to area and volume size, LA strain measurements may be taken but these are not routinely performed during standard TTEs. LA strain is measured using a type of speckle-tracking echocardiography (STE) technique which focuses on the subtle longitudinal changes within the myocardium to analyse myocardial deformation (Gan, et al., 2018). Strain imaging of the LA produces three functional strain values (contractile, conduit and reservoir) which correspond to different stages of the cardiac cycle (Jarasunas, et al., 2018). As patients in AF lack normal atrial contraction and have a loss of atrial kick, it is expected that the contractile strain, associated with LA contraction, is not present. However, the conduit and reservoir functions can still be compared across all three study groups to create a scale to suggest and predict whether a patient is likely to develop AF in the future; prior to any changes in LA size. Furthermore, this can then be further compared to determine whether there are any significant differences in strain patterns between the different groups of AF.

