The correlation between AF and a dilated LA are widely recognised, however, LA enlargement may be both a cause and consequence of AF. Dilation of the LA has been largely suggested to be due to atrial remodelling as a result of a change in atrial function and structure – as seen in the case of AF. However, there are other factors which affect atrial function and structure which ultimately result in atrial remodelling. This includes pathologies such as mitral valve disease (mitral stenosis, regurgitation, or a mixed disease), structural cardiac disease (such as heart failure, cardiomyopathies, and congenital disease) and hypertension (Van De Vegte, *et al.*, 2021). As hypertension can also cause atrial remodelling and is a risk factor for AF, patients that are in normal sinus rhythm (NSR) that have controlled hypertension are included in this study as a disease-control group. It is expected that the atrial strain values of these patients will fall between those of the control group (NSR) and of those in the disease group (chronic AF).

Existing available literature (see document Literature Review Table) suggests that there is a significant difference in the strain values between patients in NSR to those in AF. However, limited studies have included hypertensive patients or investigated

the differences in strain values between AF patients. Furthermore, previous studies have been limited by method technique. This is because many studies have either used external STE software to create atrial strain values or have adopted global longitudinal strain (GLS) methods to track the LA. This is a significant limiting factor as GLS methods are intended to assess longitudinal function of the left ventricle.

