# 1.1 Background

From the current literature available (*see document Literature Review Table*), it has been suggested that there is a correlation between AF and LA strain values. Existing literature suggests that patients in AF have a reduced LA strain value compared to patients in NSR. However, there are limited studies which also include controlled hypertensive patients despite collecting data regarding blood pressure. Furthermore, the majority of literature reviewed appears to focus on patients that have other comorbidities, and it could be argued that these can affect the parameters measured and analysed. This includes studies involving patients with valvular pathologies such as aortic stenosis and aortic valve replacements as well as studies involving patients with potential structural heart deformations such as those seen with heart failure or following a myocardial infarction. These factors may alter strain patterns and LA size as a result. By listing these factors as exclusion criteria, this study should minimise any external and uncontrollable factors which may affect LA strain value and LA size.

Furthermore, some studies do not have a standardised zero-reference point as some studies used the P wave for NSR and the R wave for AF patients which may cause a discrepancy in results. In this study, it has been agreed that the zero-reference point will be the R wave to create R-R cycles. This is because the P wave is not present in AF and thus cannot be used as a definitive reference point within the AF group. Both groups will have R waves present and therefore, the reference-point can be standardised across all three groups. Additionally, many of the studies reviewed appear to focus on only one LA strain and phase within the cardiac cycle. However, some do include all three. This study will include all three strain values as well as peak atrial longitudinal strain (PALS) values. However, statistical analysis may not be doable for the contractile phase as this is not present in patients with AF. The biggest pitfall that is common to most, if not all, studies reviewed is that the methods used to calculate LA strain were originally designed to measure global longitudinal strain (GLS) of the left ventricle (LV). This study utilises the automated function imaging (AFI) LA atrial strain tool provided by GE Healthcare which is specific to the LA as opposed to GLS methods to track the LV.

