# 2. Study Outline

## 2.1 Aims and Objectives

The aims of this research project are split into two sets of comparisons. The first is to determine whether there is a statistically significant difference between atrial strain values in normal sinus rhythm (NSR) patients (control group), to controlled hypertensive patients (disease-control group) and patients with established, chronic AF (disease group). Atrial strain values from these groups will also be compared to left atrium (LA) area and volume to determine correlation. Furthermore, providing there is a significant difference, atrial strain values between AF groups PAF, persistent, and permanent can also be compared to potentiate deterioration of atrial strain.

Null hypothesis: There is no significant difference between the atrial strain measurements in patients with normal sinus rhythm to patients with chronic atrial fibrillation and no correlation between atrial strain measurements and left atrium are and volume size.

Research / alternative hypothesis: There is a statistically significant difference between atrial strain values between patients with normal sinus rhythm and patients with atrial fibrillation and this correlates with changes seen in left atrium area and volume size.

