#### 2.2.6 Statistical Analysis Plan

Continuous data normality will be assessed utilising the Shapiro-Wilk test. Nonparametric data will be analysed via Mann-Whitney U tests and Kruskal-Wallis oneway ANOVA tests. If data shows a normal distribution, to compare the LA strain values between the control (NSR) and disease (AF) groups an independent T-test can be performed; this will establish whether there is an initial statistically significant difference between the two. Following this, to compare the mean strain values for each phase between the three groups, a one-way ANOVA must be performed. A one-way ANOVA can also be performed to determine any significant differences between the strain values between AF groups. These data analysis methods will also be repeated to analyse LA area and volume. To assess whether LA area and volume size correlate with LA strain, a Pearson correlation coefficient must also be performed. Furthermore, to determine whether LA strain may be used as an early predictor of AF, linear regression models must be adapted. For categorical data, such as gender, chisquared tests will be performed to determine any significant difference between groups. All statistical tests will be performed using the Prism GraphPad software.

It is expected that there will be a significant difference in strain values between NSR and AF participants. It is also expected that an increase in LA area and volume size will correlate with a decrease in LA strain values.

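### The sample size of 234 and its 85% power rest on contractile strain in AF, a comparison the protocol doubts it can make; no planning inputs are given for the strain measures that can be compared

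*Combined protocol and SAP*

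**What the plan says.** Section 2.2.5 (Power Calculation) says the sample size calculation "involved detecting the smaller difference of left atrium contractile % between subjects with atrial fibrillation and healthy volunteers". It gives an expected difference of 4.0, an SD of 7.5, alpha 0.05, power 0.85 and a one-way ANOVA at three levels. The result is at least 78 per group and 234 in total. The G*Power output in the Appendix shows an effect size f of 0.2177324 and actual power of 0.8509156.

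For patients in AF, section 1 (Introduction) says "it is expected that the contractile strain, associated with LA contraction, is not present". It adds that "the conduit and reservoir functions can still be compared across all three study groups". Of the controlled hypertensive group it says: "It is expected that the atrial strain values of these patients will fall between those of the control group" and those of the AF group.

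Section 1.1 (Background) says "This study will include all three strain values as well as peak atrial longitudinal strain (PALS) values", and then warns that "statistical analysis may not be doable for the contractile phase as this is not present in patients with AF".

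The null hypothesis in section 2.1 is about strain in general and names no phase: "There is no significant difference between the atrial strain measurements in patients with normal sinus rhythm to patients with chronic atrial fibrillation". Section 2.2.6, for normally distributed data, plans an NSR-versus-AF t-test and then says "to compare the mean strain values for each phase between the three groups, a one-way ANOVA must be performed". Kruskal-Wallis and Mann-Whitney tests are the alternatives for non-normal data. No rule is given for contractile strain in the AF group.

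**The concern.** The one contrast used to justify the sample size needs a contractile value in the AF group. The protocol's own text expects that value not to exist. The measures that can be compared across all three groups have no expected difference, SD or power figure in the documents.

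Two things are at stake. First, a null result for reservoir or conduit strain could not be judged against any stated expected effect, because the 85% was worked out for a different measure. Second, section 2.2.6 still asks for every phase to be compared across the three groups. What to do with contractile strain in AF would then be decided after the data are seen.

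**Working it through.** **Inputs.** Section 2.2.5: difference 4.0, SD 7.5, alpha 0.05, power 0.85, three groups, 78 per group. Appendix: f = 0.2177324, λ = 11.0933, critical F = 3.0349 on 2 and 231 df. The position of the hypertensive mean is not stated in section 2.2.5. Placing it midway reproduces the printed f, so midway is inferred.

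**Step 1: reproduce the plan's figure.** Take group means of 0, 2 and 4.
- f = √[((−2)² + 0² + 2²)/3] / 7.5 = 1.6330/7.5 = 0.21773
- λ = f² × N = 0.047407 × 234 = 11.093
- Critical F(2, 231) = 3.0349
- Power from the noncentral F distribution = 0.8509; at N = 231 it is 0.8460

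This matches the Appendix. (The figure captions give f = 0.25, which would need only 180 participants. They do not describe the run that produced 234. That is a separate matter.)

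**Step 2: what 78 per group can detect on any measure.** With the middle group midway, f = (range/SD) × √(1/6).
- 4.0/7.5 = 0.533, so 85% power corresponds to a range of about 0.533 SD between the extreme group means.
- If the hypertensive mean sits at one end instead, f = (range/SD) × √2/3, and about 0.461 SD is enough. A range of 0.533 SD therefore suffices wherever the middle group lies.
- The two-group NSR-versus-AF t-test, 78 against 78, needs about 0.483 SD. At 4.0/7.5 its power is 0.911.

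**Step 3: does choosing the smallest difference cover the other measures?** Power depends on the difference divided by the SD, not on the raw difference. Suppose, purely as an assumption, that another phase had a difference of 5, which is larger than 4.0. Midway ANOVA power would fall below 85% if its SD exceeded 5/0.533 = 9.4, and would be above 85% if its SD were smaller. The documents give neither figure for any other phase, so the question stays open in both directions.

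**Step 4: what remains for contractile strain if AF has no value.** Only NSR versus hypertension is left. The implied midpoint difference is 4.0/2 = 2.0.
- Standardised difference = 2.0/7.5 = 0.267
- Noncentrality = 0.267 × √(78/2) = 1.665
- Two-sided t-test power = 0.380
- For 85% power the difference would have to be about 0.483 × 7.5 = 3.6 points

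**The case against.** The strongest defence is that section 2.2.5 describes a deliberate worst case. The literature was consulted, statistical support was given, and the lowest difference was used so that every other measure would be covered. That may turn out to be true. It is not shown, because no competing values are listed and a smallest raw difference need not be the smallest standardised one (Step 3).

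Other points carry weight:
- The effect size f is unit-free, so 78 per group gives 85% for any measure whose expected range reaches 0.533 SD. This stands, but no section says that reservoir strain, conduit strain or PALS is expected to reach it.
- The Literature Review Table cited in sections 1 and 1.1 is a separate document and was not available here. It may hold the missing values. This limits the point to what sections 2.2.5 and 2.2.6 state.
- Read together, sections 1 and 1.1 show the intent to concentrate on conduit and reservoir strain. The instruction in section 2.2.6 does not carry that through.
- The stated null hypothesis is NSR versus AF, where the t-test needs only 0.483 SD. That gives some slack, but an expected effect is still needed to claim 85%.

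A reader might infer that the study is underpowered or that 234 is too small. The documents do not support that: they contain no inputs for the measures that can be compared, and the arithmetic behind 234 is correct. A reader might also suppose that contractile strain in AF will be scored as zero, which would rescue the calculation. No section says so, and section 1.1 treats the analysis as possibly not feasible.

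**Conclusion.** The point holds as a fault in the stated justification and should be fixed. The 85% power belongs to a comparison that the protocol doubts it can make, and section 2.2.6 conflicts with sections 1 and 1.1 by asking for that comparison anyway. For reservoir strain, conduit strain and PALS, power at 78 per group is not shown and could be above or below 85%. The one firm figure is a detectable range of about 0.533 SD, which assumes a three-group one-way ANOVA, alpha 0.05, a common SD, equal groups and the hypertensive mean midway. The 38% for NSR-versus-hypertension contractile strain rests on the same inferred midpoint. Treating PALS as comparable in AF is a reading of section 1.1, which flags only the contractile phase; the Introduction names conduit and reservoir explicitly.

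**What to change.** **Section 2.2.5.** Name one planning measure that can be measured in all three groups. Choose it in advance, and not by which gives the best power. Reservoir strain is an example, since the Introduction says it can be compared across the groups. Take its NSR-versus-AF difference and SD from the sponsor's literature table, state the assumed hypertensive mean, and restate the power at 78 per group with N kept at 234. Until those inputs are given, replace the contractile-based statement with: *78 per group gives 85% power to detect a range of 0.533 SD between group means (three-group one-way ANOVA, alpha 0.05, middle group midway).* Add that this is a detectable effect, not an expected one. On its own, that sentence does not close the gap.

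**Section 2.2.6.** Limit the NSR-versus-AF test and the three-group comparison (ANOVA or Kruskal-Wallis) to reservoir strain, conduit strain and PALS. Leave the whole chronic AF group out of the contractile comparison, whatever the rhythm at the scan, so that the group is not split by scan rhythm without a stated analysis. Label NSR-versus-hypertension contractile strain exploratory and report its limited power.

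**Cost.** One G*Power run and a wording amendment. The sample size, groups and data collection do not change. The restated power may come out below 85%. Any contractile values from AF-group participants who happen to be in sinus rhythm at the scan would not be used in that comparison.

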#### 2.2.6 Statistical Analysis Plan

Continuous data normality will be assessed utilising the Shapiro-Wilk test. Nonparametric data will be analysed via Mann-Whitney U tests and Kruskal-Wallis oneway ANOVA tests. If data shows a normal distribution, to compare the LA strain values between the control (NSR) and disease (AF) groups an independent T-test can be performed; this will establish whether there is an initial statistically significant difference between the two. Following this, to compare the mean strain values for each phase between the three groups, a one-way ANOVA must be performed. A one-way ANOVA can also be performed to determine any significant differences between the strain values between AF groups. These data analysis methods will also be repeated to analyse LA area and volume. To assess whether LA area and volume size correlate with LA strain, a Pearson correlation coefficient must also be performed. Furthermore, to determine whether LA strain may be used as an early predictor of AF, linear regression models must be adapted. For categorical data, such as gender, chisquared tests will be performed to determine any significant difference between groups. All statistical tests will be performed using the Prism GraphPad software.

It is expected that there will be a significant difference in strain values between NSR and AF participants. It is also expected that an increase in LA area and volume size will correlate with a decrease in LA strain values.

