#### 2.2 Method

Patient selection:

Potential candidates for this study will have been referred for a TTE by a healthcare professional. The referrals will be reviewed and if the patient meets the initial eligibility criteria, they will be considered as part of this study. The initial eligibility criteria consist of being over the age of 50 (although patients will be age-matched across the three groups) and falling within the control (normal sinus rhythm), disease-control (controlled hypertension) or disease groups (chronic AF).

Data collection:

The images obtained from the TTE scan will be stored on the ultrasound machine as well as the picture archiving systems (PACS) on the computer. The measurements to be compared are:

- Left atrium area
- Left atrium volume
- Left atrium strain measurement and analysis using the R wave

The first two measurements are routinely performed during TTEs, but atrial strain measurements are not routinely performed. This additional measurement will not affect or delay the TTE results and report from being sent back to the referrer or delay any further correspondences with other healthcare professionals. Atrial strain measurements will be conducted using the AFI LA atrial strain tool provided by GE Healthcare. These three measurements will be compared across the three groups and tested for a statistically significant difference. Providing that there is a significant

difference, particularly between the control and disease groups, a subsequent comparison will be conducted between the three groups of AF using the existing data.

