#### 2.2.4 Eligibility Criteria

Patients must be in one of the following categories to be included: normal sinus rhythm, normal sinus rhythm with controlled hypertension and chronic atrial fibrillation (persistent or permanent). Patients with paroxysmal AF may also be included but only as part of subsequent analysis when comparing strain measurements between AF groups. Additionally, eligible patients must conform to the following inclusion and exclusion criteria.

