#### Inclusion criteria:

- Criterion 1: subjects will be included in the study if they are within one of the following groups:
  - Known to be in normal sinus rhythm, are normotensive and have no underlying health problems.
  - Known to be in normal sinus rhythm and have controlled hypertension. This must have been diagnosed by a healthcare professional and the patient should be taking appropriate antihypertensive medication.
  - Known to have chronic atrial fibrillation (persistent or permanent AF). This must have been diagnosed by a healthcare professional and the patient should be appropriately anticoagulated.
- Criterion 2: subjects should ideally be ≥ 50 years, but subjects will be age matched across all three groups.
- Criterion 3: patients should have an EF  $\ge$  50%.
- Criterion 4: good quality TTE images.
- Criterion 5: No valvular pathologies.
  - Patients with AF that have < moderate valvular pathologies may be considered (as per the British Society of Echocardiography Guidelines).

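### Section 2.2.6 makes no provision for unequal variances, so the AF-type ANOVA, whose group sizes are uncontrolled, can miss its nominal 5% error rate if both spreads and sizes differ

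*Combined protocol and SAP*

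**What the plan says.** Section 2.2.6 opens with the selection rule: "Continuous data normality will be assessed utilising the Shapiro-Wilk test". If normality fails, "data will be analysed via Mann-Whitney U tests and Kruskal-Wallis" methods apply. If it holds, sinus rhythm and AF are compared by an independent t-test and the three main groups by one-way ANOVA. The same methods are repeated for LA area and volume. For AF types: "A one-way ANOVA can also be performed to determine any significant differences between the strain values between AF groups". No section mentions equality of variances, a variance check or a Welch-type test, and Section 2.2.5 plans with one common SD of 7.5.

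The sizes of the AF-type groups are left open:
- Persistent and permanent AF form one disease group of at least 78 (Sections 2.2.4 and 2.2.5), with no split between them.
- Paroxysmal patients are optional and have no target: "Patients with paroxysmal AF may also be included but only as part of subsequent analysis when comparing strain measurements between AF groups".
- Section 2.2 makes the analysis conditional on a significant main result and says that "a subsequent comparison will be conducted between the three groups of AF using the existing data".

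On the contractile phase, the Introduction says of AF patients that "it is expected that the contractile strain, associated with LA contraction, is not present". Section 1.1 warns that this phase may not be analysable, but Section 2.2.6 still plans a three-group comparison for each phase.

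**The concern.** The plan checks normality, but the ordinary t-test and ANOVA also assume equal variances, and that assumption is unprotected. Its failure matters little when groups are the same size. It matters when sizes differ, because the pooled variance is then dominated by the largest group. If that group has the smallest spread, the F test rejects too often. If it has the largest spread, the test rejects too rarely.

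The AF-type comparison is where unequal sizes can arise, since nothing in the plan controls them. At stake is the claim in Sections 2.1 and 2.3 that strain declines as AF becomes more established: a false decline could be reported, or a real one missed.

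The normality check has a separate, smaller drawback. One phase may be compared on means and another on ranks because of chance results in the check, which makes the phases harder to read together.

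**Working it through.** **The plan's own figure.** Inputs from Section 2.2.5 and Appendix Figure 1: difference 4.0, SD 7.5, three groups, alpha 0.05, power 0.85. With means 0, 2 and 4, f = √(8/3)/7.5 = 0.2177. Then λ = f² × 234 = 11.09, critical F(2, 231) = 3.035, power 0.851. This matches the appendix, so 78 per group is reproduced under a common SD.

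**Assumed inputs.** The documents give no SD or size by AF type. The first three rows of the table below use chronic AF groups that add to the planned 78 (25 + 53 and 20 + 58) plus 15 or 20 paroxysmal patients. SD ratios are 9/5 = 1.8 and, in the milder case, 8/6 = 1.33.

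**Why the F test drifts.** With no true difference, the expected between-group mean square is Σ(1 − nᵢ/N)σᵢ²/(k − 1), and the expected within-group mean square is Σ(nᵢ − 1)σᵢ²/(N − k). They should be equal.
- 15/25/53 with SD 9/7.5/5: between = (67.9 + 41.1 + 10.8)/2 = 59.9; within = (1134 + 1350 + 1300)/90 = 42.0; ratio 1.43, so too many rejections.
- 15/25/53 with SD 8/6.5/6: between = (53.7 + 30.9 + 15.5)/2 = 50.0; within = (896 + 1014 + 1872)/90 = 42.0; ratio 1.19.
- 20/20/58 with SD 5/6/9: between = (19.9 + 28.7 + 33.1)/2 = 40.8; within = (475 + 684 + 4617)/95 = 60.8; ratio 0.67, so too few rejections.
- 78/78/78 with SD 8/7/4: both equal (64 + 49 + 16)/3 = 43; ratio 1.

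**Simulated type I error at nominal 5%** (normal data, no true difference, at least 60,000 replicates per row):

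| Sizes | SDs | Ordinary ANOVA | Welch ANOVA |
|---|---|---|---|
| 15/25/53 | 9/7.5/5 | 12.2% | 5.1% |
| 15/25/53 | 8/6.5/6 | 8.1% | 5.0% |
| 20/20/58 | 5/6/9 | 1.5% | 4.9% |
| 20/20/60 | 7.5 each | 5.0% | 5.0% |
| 26/26/26 | 5/7.5/10 | 5.6% | about 5% |
| 78/78/78 | 8/7/4 | 5.4% | 5.1% |

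Sensitivity to the assumptions: 20/20/60 with SDs 6, 7.5 and 9 gives 2.5% or 9.4%, depending on which group has which SD. Sizes 30/28/20 with a 1.5:1 ratio give 4.2% to 6.4%.

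**Kruskal-Wallis** in the first three rows, with fewer replicates (6,000): about 8% to 9%, about 6% and about 2.5%. It reduces the distortion but does not remove it.

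**Role of the pre-test.** The full two-stage rule was simulated at 15/20/58, with Shapiro-Wilk applied in each group. With SDs 10/7.5/5 it gives 14.4%, against 14.8% for ANOVA alone. With SDs 5/7.5/10 it gives 1.4%, against 1.1%. The pre-test barely changes the error rate. Its own false-alarm rate, if each of three normal groups is tested at 5%, is 1 − 0.95³ = 14.3% per outcome. Section 2.2.6 does not say whether the check is made group by group, so this figure is also conditional.

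**The case against.** The strongest reply is that the error rates come from invented inputs. That stands: neither the SD ratio nor the imbalance is in the documents, and the absence of a size target does not prove that sizes will be unequal. A reader might take 1.5% to 12% as a property of the plan or as bounds. It is neither. Milder inputs give less, equal spreads or sizes give about 5%, and more extreme ones give more.

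A reader might also blame the Shapiro-Wilk step. The two-stage simulation does not support that.

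A reader might infer that the protocol itself implies unequal spread, because contractile strain vanishes in AF or because paroxysmal patients may be scanned in sinus rhythm. The first concerns only the contractile phase, which Section 1.1 already flags. The Introduction says that the conduit and reservoir phases remain comparable, and nothing says that their spreads differ. The second is not stated anywhere.

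The comparison is also conditional and secondary, and the sample size was not built for it. That limits the consequence but does not remove the gap.

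Finally, Welch's ANOVA is not a cure for everything. In simulation with strongly skewed data and small groups it reached 8.3%. With equal SDs and the same skew it gave 6.7%, against 4.7% for the ordinary ANOVA. It is undefined if contractile strain is recorded as zero for every AF patient. These points stand and narrow the remedy.

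**Conclusion.** The gap holds in conditional form. Section 2.2.6 gives no protection against unequal variances, and the AF-type comparison has no size targets. If spreads and sizes both differ, its ordinary ANOVA can run at about 1.5% or about 12% instead of 5%, given assumed sizes near 15-20/20-25/53-58 and SDs 1.8:1, or at about 8% with SDs 8/6.5/6. The direction depends on whether the largest group has the largest or the smallest spread.

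A reader might infer that the main three-group result is unsafe as well. At the planned 78 per group it is not: 5.4% with SDs 8/7/4. It would become exposed only if recruitment missed the minimum unevenly. For example, an assumed 60/70/104 gives 8.3% with SDs 8/7/4 and 3.6% with SDs 4/7/8.

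The cause is the missing variance protection. The pre-test's own drawback is inconsistency of method between phases. The issue is worth correcting because the correction is cheap, but it is not a threat to the primary comparison as designed.

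**What to change.** In Section 2.2.6:
- Prespecify Welch's t-test for sinus rhythm versus AF, and Welch's one-way ANOVA with unequal-variance pairwise confidence intervals for the three-group comparisons (main groups and AF types). Apply them to reservoir strain, conduit strain, PALS, LA area and LA volume.
- Stop choosing the test by Shapiro-Wilk. Keep Mann-Whitney and Kruskal-Wallis as sensitivity analyses.
- State that a markedly skewed outcome will be analysed on a transformed scale, and fix the rule for this before groups are compared.
- Exempt contractile strain from any comparison in which it is absent or constant in AF, consistent with the caution in Section 1.1.
- Report the size and SD of each AF-type group beside its result.

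The cost is a change of wording. At the planned design (difference 4.0, SD 7.5, 78 per group), simulated power is 85.2% for the ordinary ANOVA and 84.8% for Welch's, a loss of 0.4 points, so the sample size need not change. The remaining downside is some loss of error control under strong skew with small groups, which the transformation rule and the rank-based sensitivity analyses are there to address.
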